

67. Borg G. *Borg's perceived exertion and pain scales*. Champaign, IL: Human Kinetics; 1998.

68. Bandura A. *Social foundations of thought and action: a social cognitive theory*. Prentice Hall, 1986.

70. Cohen J. Statistical power analysis for the behavioral sciences, second edition. 1988. Hillsdale NJ: Lawrence Erlbaum Associates.

Statistical Design and Power

The proposed Phase-I/II clinical trial will use a parallel group, randomized controlled trial (RCT) design. The primary study outcomes involve the oral Symbol Digit Modalities Test (SDMT) as a measure of cognitive processing speed (CPS) and thalamocortical resting-state functional connectivity (RSFC) measured using fMRI. The exploratory study outcomes involve functional outcomes that are associated with CPS in persons with MS (i.e., community integration, ability to perform activities of daily living, quality of life, and functional mobility).

Sample Size Considerations. As described in the original application (i.e., R01HD091155-A1), we conducted a conventional power analysis using G*Power (Version 3.1.9.5) and estimated the appropriate sample size for detecting differences in follow-up SDMT scores, controlling for baseline score (Specific Aim 1). Using G*Power, this was accomplished using the 'F test' selection within the 'Test' family menu, and the Statistical Test of 'ANCOVA: Fixed effects, main effects and interactions'. The effect size ($\eta_p^2=0.11$) for the power analysis was computed from our pilot RCT¹² of TMWX training compared with a waitlist control condition on SDMT scores in persons with MS who had mild ambulatory disability, but not CPS impairment. That effect size was smaller than the effect sizes for thalamocortical RSFC outcomes, and thus was included in the main power analysis as a conservative approach. The power analysis included standard assumptions of alpha (0.05) and beta (0.80). The power analysis indicated that the minimal total sample size for testing group differences on follow-up SDMT scores, controlling for baseline scores should be 66 participants (33 per group). This supports our goal of recruiting 88 participants (44 per condition) as yielding adequate power, based on retention of 75% of the enrolled participants. The current application proposes a change of grantee organization whereby the final 72 participants will be enrolled at KF. We will explore the possible influence of study site on the outcomes in *post-hoc* sensitivity analyses. We expect that the effects of study site are likely negligible given the constants of the study team and standardized manuals of operating procedures that guide all study aspects.

Statistical Analysis. The data analyses will be overseen by [name] and follow intent-to-treat principles (i.e., include all persons regardless of dropout). In the case of a drop-out, missing data will be imputed by carrying the last observed value forward. We further will perform exploratory data analyses only in those who completed follow-up testing (i.e., completer's or per protocol analysis) and in those who demonstrated good adherence (i.e., attended at least 83% of sessions) and compliance. The analytic plan will account for several potential confounders of the effects of progressive TMWX training on the outcome measures. These include MS duration, BMI, age, sex, cognitive reserve, T2-lesion volume, and relapse rate. If these variables differ between groups, they will be included as additional covariates in the following analyses.

Specific Aim 1. The primary analysis will involve a statistically efficient step-down testing approach using ANCOVA models to examine changes in CPS and thalamocortical RSFC (i.e., examining group differences in follow-up outcomes, adjusting for baseline). As the primary study outcome involves CPS based on SDMT scores, we will first perform an ANCOVA model on follow-up SDMT score, with group (exercise or control) as a between-subjects factor and baseline SDMT score as the covariate. If statistically significant (i.e., $p<.05$), we will then assess the effects of the intervention on thalamocortical RSFC. This second step will involve performing two separate ANCOVA models on follow-up RSFC between the thalamus and right MFG and ACC, respectively, with group (exercise or control) as a between-subjects factor and baseline RSFC between the thalamus and right MFG and ACC, respectively, as the covariates. We will require an alpha of .05 (corrected for multiple comparisons) for significance for thalamocortical RSFC outcomes. The correction for multiple comparisons will be achieved by establishing a suitable voxel cluster-level threshold through Monte Carlo simulations (using the 3dClustSim program, part of the AFNI suite of image analysis programs). Based on our pilot work¹², we expect significant group differences in SDMT score and RSFC between the thalamus and right MFG and ACC, respectively, at follow-up after controlling for baseline scores, whereby participants who are randomly assigned to the exercise group will demonstrate greater SDMT scores and stronger thalamocortical RSFC at follow-up compared with those who are randomly assigned to the control group.

Specific Aim 2. We will examine RSFC between thalamus/right MFG, and RSFC between thalamus/ACC, respectively, as two potential mediators of the effects of TMWX training on CPS, consistent with the methodologies of Baron and Kenny⁸⁹ and MacKinnon et al⁹⁰. This statistical mediation approach is consistent with the proposed gold standard approach for examining exercise-related mechanisms of cognitive

improvement at the brain-systems level in the general population²⁸. As pre-conditions of the mediation analysis, we will first perform correlations among group (i.e., exercise or control), change in SDMT scores, and change in RSFC between the thalamus and right MFG and ACC, respectively, using Spearman's rho rank-order correlations (ρ)⁹¹ to test if those outcomes are interrelated. Consistent with our pilot work¹², we expect that TMWX training will be associated with improvements in CPS and increases in thalamocortical RSFC. Moreover, we expect that improvements in CPS will be associated with increases in thalamocortical RSFC. Then, to establish mediation, we will perform hierarchical linear regression models for evaluating each of the two mediators (i.e., changes in RSFC between thalamus/right MFG, and RSFC between thalamus/ACC, respectively), separately. This will involve regressing change in SDMT score on group in Step 1 and then adding change in the mediator in Step 2. In order to establish mediation, if the pre-conditions are met, group must influence change in SDMT in Step 1, and the mediator must influence change in SDMT score in Step 2 of the regression as well as attenuate the effect of group on SDMT scores (i.e., the effect of group on SDMT should be reduced and become non-significant between Step 1 and Step 2)⁸⁹. As such, we expect significant effects of group on change in CPS, and that the effect of group (i.e., exercise or control) on change in CPS will be attenuated, but not reach zero, when accounting for the effects of changes in thalamocortical RSFC. In other words, we expect that changes in thalamocortical RSFC will be partial mediators of the effects of TMWX training on CPS in persons with MS with impaired CPS.

Exploratory Aim 3. Considering that MS-related CPS impairment substantially limits daily functioning, we now include exploratory functional outcomes in this proposal, as suggested by reviewers. As there are multiple, interrelated outcomes within this Exploratory Aim, we will perform a multivariate analysis of covariance (MANCOVA) on follow-up scores for the functional outcomes controlling for baseline values as an approach for examining the consistency of the potential intervention effects (i.e., exercise vs. control as the between-subjects factor) on this overall construct (i.e., how functional consequences of CPS impairment may change together with TMWX training). We further will explore the effects of the intervention on the individual outcomes using separate exploratory, descriptive, univariate ANCOVA models on follow-up CIQ scores (i.e., community participation), TIADL scores (i.e., ability to perform activities of daily living), MSIS-29 scores (i.e., QOL), T25FW and LSPA performance (i.e., functional mobility), respectively, with group (exercise or control) as a between-subjects factor and baseline CIQ, TIADL, MSIS-29, T25FW, and LSPA scores, respectively, as the covariates. We expect significant and consistent group differences in those functional outcomes at follow-up after controlling for baseline scores, whereby participants who are randomly assigned to the exercise group will demonstrate better follow-up scores on functional outcomes compared with those who are randomly assigned to the control group.

As MS-related cognitive impairment involves reduced performance in other cognitive domains beyond CPS, we now include exploratory cognitive outcomes beyond the SDMT in the current proposal, as suggested by reviewers. We will adopt a similar approach (see *Exploratory Aim 3 above*) to examine the effects of the intervention on the general construct of cognitive performance using MANCOVA and on the individual cognitive tests using separate univariate ANCOVA models. Effect sizes will be expressed as partial eta-squared (η_p^2) and Cohen's d ⁹². The effect sizes from the interaction terms from the ANCOVAs and correlations will serve as effect sizes for the subsequent power analyses required for informing the development of a home-based rehabilitation program using this intervention approach.

Analysis by Race/Gender. We anticipate that 70% of participants will be female and 70% will be Caucasian. We will test the effects of gender and race on the intervention effects, and if there are interactions, we will separately analyze by gender/race to explore the specific effects of the variables on the outcomes. We do recognize that we will not likely enroll sufficient numbers of male participants or participants of Hispanic ethnicity and or other races to make meaningful comparisons.

Treatment of Missing Data. We conservatively plan for approximately 25% attrition based on a previous large RCT of 6-months (i.e., a longer intervention period than the proposed study) of multimodal exercise training versus a stretching-and-toning control condition on mobility outcomes in persons with moderate-to-severe MS-related ambulatory disability in our laboratory⁵⁶. In that study, the adherence rates for both the exercise and stretching-and-toning conditions were upwards of 75%, despite a significant barrier to participation being the inclusion of persons with substantial ambulatory disability. Of note, those adherence rates are *lower* than the overall average adherence rates for exercise trials involving persons with MS, based on a recent systematic review (i.e., upwards of 84% for both exercise and control conditions)⁵⁷. Nevertheless we have plans for

exploring and examining the impact of such losses, as we could have upwards of 25% drop-out, given that this sample includes persons with objective CPS impairment. Initially, analyses will be done on the data set using last observation carried forward and then on the actual data collected (case-wise deletion), followed by multiple imputation for missing data. All analyses at present are planned using SPSS software (version 25 or higher), although as new options continue to evolve with SAS or R; these will be considered if there are new tools for imputation that will help understand the impact of missing data. We believe that these imputations should involve fewer than 15% of the participants, which then should have minimal impact on the analyses. However, it is important to assess this from a best case and worst case scenario and if the results are consistent, then we can be more confident of our findings. If these analyses yield differing results – more exploratory analyses are required to understand if the differences in the outcomes are coming from the control condition or the intervention condition. If the control condition, the implications can be examined in one way and if the intervention condition, it is likely to add cautionary notes to the findings.

Interim and Final Analysis. We do not plan any interim efficacy or futility analyses. The study team will work together for publications on the protocol, fidelity monitoring plan, as well as the primary study outcomes.

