STUDY PROTOCOL AND STATISTICAL ANALYSIS PLAN

Study Title: Exercise Training Effects on Cognition and Brain Function in Multiple Sclerosis: A Systematically-Developed Randomized Controlled Trial

NCT Number: NCT03677440

Date: 5/21/2020

Study Protocol

1. Abstract

Slowed cognitive processing speed (CPS) is a common and debilitating consequence of multiple sclerosis (MS) that is notoriously difficult to treat. As such, we undertook a systematic line of research that indicated that supervised, progressive treadmill walking exercise (TMWX) training might improve CPS and brain functioning among fully-ambulatory persons with MS. The current study will be the first adequately-powered, single-blind randomized controlled trial (RCT) that examines the efficacy of 12-weeks of TMWX training compared with an active control condition on CPS, thalamocortical brain connectivity (based on resting-state fMRI), and exploratory functional outcomes in 88 fully-ambulatory persons with MS who present with slowed CPS. 65 of those persons will be recruited at Kessler Foundation. The intervention condition involves supervised, progressive TMWX training 3 times/week over 12-weeks; this initially involves 15-minutes of light-to-moderate intensity TMWX that progresses up to 40-minutes of vigorous intensity TMWX. The active control condition involves supervised, minimal intensity, stretching-and-resistance exercise that will be delivered on the same frequency as the intervention condition. The primary study outcomes involve Symbol Digit Modalities Test performance (i.e., CPS) and fMRI-based measures of thalamocortical resting-state functional connectivity. Exploratory study outcomes involve measures of community participation, activities of daily living, quality of life, and functional mobility. All study outcomes will be administered before and after the 12-week study period by treatment-blinded assessors. If successful, the current study will provide the first Class I evidence for the effects of TMWX training as an approach for improving CPS and its neural correlate, and possibly mitigating the impact of slowed CPS on functional outcomes in MS.

2. Study Objectives

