5.1.1. Sample Size. We plan to enroll 88 fully-ambulatory persons with MS (i.e., 44 per condition) who have objective impairment in CPS; this is based on a power analysis and presumed 25% attrition. Of the 88 total participants, 65 will be recruited at Kessler Foundation, as this study is currently ongoing and was partially completed at the University of Alabama at Birmingham. The minimal sample size of 66 persons with MS (i.e., 33 per condition) was determined based on power analysis using previous effect sizes from our preliminary RCT of TMWX training on CPS outcomes (i.e., $\eta_p^2=0.11$) and standard assumptions of Type I error (0.05) and power (0.80) based on analysis of covariance (ANCOVA) on follow-up SDMT scores, controlling for baseline SDMT score [19]. We note that this rate of attrition exceeds that of the overall average of exercise training studies among persons with MS based on a systematic review [28] making our calculations conservative.

5.1.2. Recruitment. Prospective participants will be recruited directly through the community, local chapter of the National MS Society (NMSS), and our laboratory database of previous participants with MS who have inquired about participating in future studies. Advertisements for the study will be distributed through local MS centers, facilitators of local MS support groups, *MS Connection* publications, and e-mail distributions. As a backup plan, we may recruit prospective participants with MS through the North American Research Committee on Multiple Sclerosis (NARCOMS) patient registry or iConquerMS if enrollment is slow.

5.1.3. Screening. The screening process for potential participants will first involve a phone screen, followed by an in-person screen. Via telephone, the project coordinator will obtain the following information from potential participants:

- Age between 18-59 years
- Definite diagnosis of MS
- Relapse-free for 30 days, not acutely taking corticosteroids
- No major depressive disorder, schizophrenia, bipolar disorder I or II, substance abuse disorder
- Not currently taking medications that can affect cognition (i.e., benzodiazepines, anti-psychotics)
- Not having known/diagnosed cardiovascular, metabolic, or kidney disease
 - If the prospective participant does report having known/diagnosed cardiovascular, metabolic or kidney disease, then physician's approval will be required in order to be eligible for study enrollment.

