The primary analysis will involve a statistically efficient, hierarchical step-down testing approach using ANCOVA models to examine differences in post-test outcomes of CPS and thalamocortical RSFC (i.e., examining group differences in follow-up outcomes, adjusting for baseline as covariate). The hierarchical step-down approach presents a series of conditional hypothesis tests after the primary hypothesis is assessed. This *a priori* specifies the importance and order of the testing so that each hypothesis is tested in order, until the first non-significant result occurs. Once a null-hypothesis is not rejected, all formal testing will stop, and all subsequent results will be reported as *post-hoc* and/or descriptive. This protects against Type I error as it assumes that the outcomes are correlated, and the overall *p*-value is protected by reporting the largest *p*-value for all the tests. As the primary study outcome involves CPS based on SDMT scores, we will first perform an ANCOVA model on follow-up SDMT score, with group (intervention or control) as a between-subjects factor and baseline SDMT score as the covariate. If statistically significant (i.e., *p*<.05), we will then assess the effects of the intervention on the general construct of CPS using MANCOVA and on the individual CPS tests using separate, univariate ANCOVA models.

Regarding thalamocortical RSFC, the next set of analyses will involve performing ANCOVA models on follow-up RSFC between the thalamus and frontal cortical areas (e.g., SFG, MFG [21]), respectively, with group (intervention or control) as a between-subjects factor and baseline RSFC between the thalamus and frontal cortical areas, as the covariates. We will require an alpha of .05 (corrected for multiple comparisons) for significance for thalamocortical RSFC outcomes. The correction for multiple comparisons will be achieved by establishing a suitable voxel cluster-level threshold through Monte Carlo simulations (using the 3dClustSim program, part of the AFNI suite of image analysis programs). Based on our pilot work [19,21], we expect significant group differences in SDMT score and RSFC between the thalamus and frontal cortical areas, respectively, at follow-up after controlling for baseline scores, whereby participants who are randomly assigned to the intervention group will demonstrate greater SDMT scores and stronger thalamocortical RSFC at follow-up compared with those who are randomly assigned to the control group.

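### The SAP calls the SDMT-based sample size conservative for RSFC, but RSFC is tested only after a significant SDMT result, so its formal power cannot exceed SDMT power

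*Combined protocol and SAP*

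**What the plan says.** The Abstract (protocol section 1) gives two primary outcomes: "The primary study outcomes involve Symbol Digit Modalities Test performance (i.e., CPS) and fMRI-based measures of thalamocortical resting-state functional connectivity". The opening of Statistical Design and Power repeats this.

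The sample size rests on SDMT only. Protocol section 5.1.1 cites "standard assumptions of Type I error (0.05) and power (0.80) based on analysis of covariance (ANCOVA) on follow-up SDMT scores". The SAP (Sample Size Considerations) uses partial eta-squared 0.11, obtains 66 participants (33 per group), and enrols 88 to allow for 75% retention. It adds that this effect was "smaller than the effect sizes for thalamocortical RSFC outcomes, and thus was included in the main power analysis as a conservative approach". It gives no RSFC effect size and no RSFC power.

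The testing rule is set elsewhere. In the SAP, Specific Aim 1, the SDMT ANCOVA comes first, and only if it reaches p<.05: "we will then assess the effects of the intervention on thalamocortical RSFC". RSFC is then tested in two ANCOVAs (thalamus with right MFG, thalamus with ACC), with this threshold: "We will require an alpha of .05 (corrected for multiple comparisons) for significance for thalamocortical RSFC outcomes". Protocol section 5.3 states the stop rule: "Once a null-hypothesis is not rejected, all formal testing will stop". That section also places a CPS MANCOVA and the individual CPS tests after SDMT and before RSFC. The SAP's Specific Aim 1 does not.

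**The concern.** A sample size set on the smaller of two effects is conservative for the other outcome only if that outcome is tested unconditionally and at the same alpha. Neither condition holds here. RSFC has to pass through the SDMT gate and then meet a corrected threshold, and neither feature enters the power calculation.

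Hypothesis 1 claims a CPS gain and increased RSFC, and the Abstract describes the trial as adequately powered. A reader would naturally apply 80% or more to RSFC and to the joint claim. If no formal RSFC result emerged, that reader would give its absence more weight than the design supports.

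**Working it through.** **Inputs from the documents.** SDMT partial eta-squared 0.11; alpha 0.05; power 0.80; ANCOVA with two groups and one covariate; 66 analysable of 88 enrolled; two RSFC regions; RSFC alpha .05 corrected by a cluster-level threshold.

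**Inputs the documents do not give (assumed, with ranges).** RSFC partial eta-squared 0.11 to 0.20, where the SAP says only that it exceeds the SDMT value. Per-test alpha .025 to .05, where .025 is an illustrative split over two regions and is not in the SAP. Correlation between the SDMT and RSFC test statistics 0 to 0.5.

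**Step 1: reproduce the plan's figure.** f² = 0.11/0.89 = 0.1236. Noncentrality λ = f² × N = 0.1236 × 66 = 8.16, with df (1, 63). Noncentral F power at alpha .05 is 0.803; at N = 65 it is 0.797. So 66 is the minimum, and 66/0.75 = 88. Both stated figures are correct.

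**Step 2: the bound.** Under the gate,

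P(formal RSFC result) = P(SDMT significant and RSFC significant) ≤ P(SDMT significant).

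This needs no assumption about RSFC. The same formula at other analysable numbers, with the 0.11 effect unchanged, gives the cap:

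| Analysable | λ | Cap (SDMT power) |
|---|---|---|
| 66 (25% loss) | 8.16 | 0.803 |
| 75 (15% loss) | 9.27 | 0.852 |
| 88 (no loss) | 10.88 | 0.903 |

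The main analysis carries the last value forward for all 88. Simulation with equal dropout in both arms and an assumed baseline-to-follow-up correlation of 0.6 to 0.9 puts the cap at about 0.76-0.78 with 25% dropout and 0.83-0.84 with 15%.

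**Step 3: how far below the cap.** For one named region at N = 66, the independent case is the product of the two powers. For example, at RSFC 0.11 and alpha .025, 0.803 × 0.711 = 0.571. The correlated case is a bivariate normal matched to the same two powers.

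| RSFC partial eta-squared | Per-test alpha | RSFC power alone | Joint, correlation 0 | Joint, correlation 0.5 |
|---|---|---|---|---|
| 0.11 | .05 | 0.803 | 0.645 | 0.691 |
| 0.11 | .025 | 0.711 | 0.571 | 0.625 |
| 0.15 | .05 | 0.919 | 0.738 | 0.765 |
| 0.15 | .025 | 0.865 | 0.695 | 0.732 |
| 0.20 | .05 | 0.979 | 0.786 | 0.796 |
| 0.20 | .025 | 0.959 | 0.770 | 0.786 |

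At 0.20 the joint figure is about 1 to 3 points below the 0.803 cap. At 0.11 it is 11 to 23 points below.

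**Step 4: the success criterion matters.** Hypothesis 1 does not say whether one region or both must be significant. With an assumed correlation of 0.5 between regions and RSFC at 0.11, SDMT plus both regions has probability 0.46-0.62, and SDMT plus at least one region 0.68-0.77. At 0.20 the ranges are 0.74-0.79 and about 0.80.

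**The case against.** The strongest reply is that the SAP reports larger RSFC effects than 0.11, so the low figures describe a case its own pilot data speak against. That stands. The 0.57-0.69 range is a lower-end scenario, 0.11 is the planned effect for SDMT and not for RSFC, and at 0.20 almost nothing is lost below the cap.

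Two stronger readings are tempting, and the documents support neither. A reader might infer that RSFC power can never exceed 80%. That ceiling belongs to 66 analysable. The SAP's Treatment of Missing Data expects imputation for fewer than 15% of participants, and better retention raises the cap. A reader might also infer that RSFC power is far below 80%. That would need an RSFC effect near 0.11 or a strict per-test threshold, and the documents establish neither. The SAP sets a cluster-level correction, and a single t-type test is only a rough stand-in for it.

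It can also be said that both documents tie the calculation expressly to SDMT, that protocol section 5.3 treats SDMT as the leading primary outcome, and that results after a failed gate are to be labelled post-hoc or descriptive. These points limit the harm. They do not make the sample size conservative for an outcome that is still named primary and can be formally tested only after another test succeeds.

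**Conclusion.** The point holds as a wording error about a stated property of the design. The sample size arithmetic is correct, and the SDMT power is not in dispute. What fails is the inference from a larger RSFC effect to a conservative sample size for RSFC, because the gate limits formal RSFC power to SDMT power: 0.803 at the planned 66 analysable, rising to 0.852 at 75 and 0.903 at 88 on completer counts.

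The bound follows from the testing rule alone; its numerical value takes the 0.11 SDMT effect as given. The size of any further loss rests on the assumed RSFC effects, per-test alphas and correlations, and should be read as a range of scenarios. If the CPS MANCOVA and individual CPS tests in protocol section 5.3 act as gates before RSFC, the probability is lower still by an amount the documents do not allow one to compute.

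**What to change.** 1. Reconcile the testing order in protocol section 5.3 with the SAP's Specific Aim 1, and say whether the CPS MANCOVA and individual CPS tests gate RSFC. No RSFC power can be stated until this is settled.
2. In Sample Size Considerations, remove the conservative argument as a justification for RSFC. State that 80% power applies to the SDMT ANCOVA only, and that formal RSFC power is bounded by it.
3. Report the pilot RSFC effect size, the per-test or cluster threshold intended, whether one or both regions are required, and the resulting joint probability.
4. Limit the description of the trial as adequately powered to SDMT.

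The cost is wording in the SAP and protocol plus one short calculation. N and the SDMT analysis stay as they are; the only downside is a less favourable stated figure for RSFC.
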